5.5.10 Study completion and post-study treatment

The patient will be accepted to complete the study on Month 12 and in visit 14 for Labelled Regime Arm, the visit number may vary according the response of the patient for Wait and Extend Arm.

The investigator must provide follow-up medical care for all patients who are prematurely withdrawn from the study, or must refer them for appropriate ongoing care.

5.5.11 Early study termination

The study can be terminated at any time for any reason by Novartis. Should this be necessary, the patient should be seen as soon as possible and treated for a prematurely withdrawn patient. The investigator may be informed of additional procedures to be followed in order to ensure that adequate consideration is given to the protection of the patient's interests. The investigator will be responsible for informing HA and/or ECs of the early termination of the trial.

6 Visit schedule and assessments

In the below table, all the required study assessments are shown and the visits for those assessments are shown with an "X" sign. The patients must be seen during their planned visit days with a ± 7 days visit window.

At a minimum, patients will be contacted for safety evaluations during the 30 days following the last study visit or following the last administration of ranibizumab, including a final contact at the 30-day point. Documentation of attempts to contact the patient should be recorded in the source documentation.

Assessment /Procedure	Phase	Screening		Main Treatment Visits / Control Visits												
	Visit for Labeled Regime Arm *	1	2	3	4	5	6	7	8	9	10	11	12	13	14	
	Visit for Wait and Extend Arm*	1	2	3	4	5	The visit numbers may vary according to the response of the patient.									
	Month	0		1	2	3	4	5	5	7	8	9	10	11	12	
Day	-7 to -1	B (1)	30	60	90	120	150	180	210	240	270	300	330	360	EoT	
Informed consent	X															
Incl/Exclusion criteria	X	X														
Randomisation		X														
Medical history	X															
Vital signs ^a	X	X	X	X	X	X	X	X	X	X	X	X	X	X	X	
Lab. Parameters (HbA1c and blood glucose)	X	X	X	X	X	X	X	X	X	X	X	X	X	X	X	
Renal Function Parameters (Urea, Creatinin, Albumin, Total Protein, Uric Acid)	X					X									X	
Pregnancy test ^b	X															
ECG (12-lead)	X														X	
Concomitant Medication	X	X	X	X	X	X	X	X	X	X	X	X	X	X	X	
Adverse events		X	X	X	X	X	X	X	X	X	X	X	X	X	X	
Treatment (injections) ^c		X	X	X	X ^d	X ^d	X ^d	X ^d	X ^d	X ^d	X ^d	X ^d	X ^d	X ^d		
Rescue Laser Treatment					X ^e	X ^e	X ^e	X ^e	X ^e	X ^e	X ^e	X ^e	X ^e	X ^e		
BCVA	X	X	X	X	X	X	X	X	X	X	X	X	X	X	X	
Ophthalmologic examination ^e	X	X	X	X	X	X	X	X	X	X	X	X	X	X	X	
Fundus photography	X														X	
FFA	X		X ^g	X ^g	X ^g	X ^g	X ^g	X ^g	X ^g	X ^g	X ^g	X ^g	X ^g	X ^g	X	
OCT	X		X	X	X	X	X	X	X	X	X	X	X	X	X	
Tonometry ^f	X	X	X	X	X	X	X	X	X	X	X	X	X	X	X	
VFQ-25	X ⁱ	X ⁱ													X	
Study Completion															X	

B=Baseline; EoT=End of the Trial; BCVA= Best Corrected Visual Acuity; VFQ-25=Visual Function Questionnaire

- a) Blood pressure and pulse will be measured after the injection of the study medication (if applicable)
- b) Urine pregnancy test will only be performed to WOCBP. Additional tests may be performed as a decision of the investigator.
- c) Site staff will contact with the patient via phone 1-3 days after the study medication injection to inquire if there is any loss of vision, eye ache, unnormal redness or occurrence of any new ocular symptom. Patients will visit the site for an unscheduled visit if needed.
- d) If the lesion is active, according to the Royal College of Ophthalmology
- e) Ophthalmologic examination: slit lamp and fundus examination will be performed before injection (if applicable)
- f) IOP measurement with tonometry will be performed before injection and after 60 minutes of injection.
- g) FFA is mandatory at month 0 and 12 and will be performed according to the investigators's desicion at the other visits.
- h) Rescue laser treatment will be performed after the first three injection and according to the criteria described in the protocol.
- i) VFQ-25 will be questioned in either of the first two screening visits.

6.1 Information to be collected on screening failures

All patients who have signed informed consent but not entered into the next epoch will have the study completion page for the screening epoch, demographics, inclusion/exclusion, and SAE data collected. Adverse events that are not SAEs will be followed by the investigator and collected only in the source data.

For all patients who have signed informed consent and are entered into the next epoch of the study will have all adverse events **occurring after informed consent is signed** recorded on the Adverse Event CRF. Adverse events will be tracked in the baseline visit (visit 2) at day 0.

Investigators will have the discretion to record abnormal test findings on the medical history CRF whenever in their judgment, the test abnormality occurred prior to the informed consent signature.

6.2 Baseline characteristics

The below information will be recorded during screening/ visit 1

- Ocular medical history: primary diagnosis and all other ocular conditions

In addition below data will be collected during Screening/Visit 1 and Baseline/Visit 2 but if all the assessments/examinations are performed during Screening/Visit 1, they should not be repeated in Baseline/Visit 2. In this case, only the VFQ-25 and injection data should be completed in the CRF:

- Related medical history: significant medical conditions and surgeries start dates and current situation.
- Concomitant medication/significant non drug treatments: all applied medication/treatments

6.3 Treatment exposure and compliance

The patients will be accepted as full compliance if the injections are performed as planned.

6.4 Efficacy

Efficacy will be evaluated per visual acuity measurements, fundus photographs, fluorescein angiography and optical coherence tomography.

Visual Acuity

Visual acuity (VA) will be evaluated for both eyes in all study visits, as best corrected visual acuity according to the protocol. VA measurements will be performed in a sitting posture with a scale like ETDRS, 4 meters away from the baseline test distance..

Color Fundus Photography and Fluorescein Angiography

Fluorescein angiography and color fundus photography will be performed together in Screening/Visit 1 and month 12. Digital fluorescein angiograms will be used for evaluations and the investigators can use their standards while diagnosing the fluorescein angiography

results. Florescein Angiography can be performed in other visits according to the investigator's decision.

Optical Coherence Tomography

Optical Coherence Tomography (OCT), will be performed to both eyes during the control visits of all patients. OCT evaluations should be performed before the study injections. Those evaluations will be performed by the trained staff in each study site. The images should be recorded to the digital video discs.

6.4.1 Appropriateness of efficacy assessments

Those efficacy assessments were based on the previous studies performed with Ranibizumab. In addition the visual acuity assessments, as well as the optical coherence tomography that will be performed in this study are standard for this indication.

6.5 Safety

Safety assessments will consist of monitoring and recording all adverse events (AEs) and serious adverse events (SAEs), ophthalmic examinations, laboratory parameters and vital signs. Information on adverse events (AEs) and serious adverse events (SAEs) will be collected at every visit.

6.5.1 Vital signs

Vital signs include BP and pulse measurements. After the patient has been sitting for five minutes, with back supported and both feet placed on the floor, systolic and diastolic blood pressure will be measured three times using an automated validated device, e.g. OMRON, with an appropriately sized cuff. The repeat sitting measurements will be made at 1 - 2 minute intervals and the mean of the three measurements will be used. In case the cuff sizes available are not large enough for the patient's arm circumference, a sphygmomanometer with an appropriately sized cuff may be used.

Vital signs will be evaluated at each visit and will be evaluated after the study injections if applicable.

6.5.2 Body Mass Index

Body Mass Index will be calculated using height in centimeters (cm) and body weight (to the nearest 0.1 kilogram [kg] in indoor clothing, but without shoes) and will only be measured only in Screening/Visit 1.

6.5.3 Laboratory evaluations

The routine laboratory assessments will be performed at all visits for clinical chemistry and for renal function parameters the assessments will be performed at Baseline/Visit 1, Month 3/Visit 5 and Month 12/Visit 14. The specimens will be obtained for the following assessments:

6.5.3.1 Clinical chemistry

HbA1c, fasting blood glucose

6.5.3.2 Renal Function Parameters

Urea, Creatinin, Albumin, Total Protein, Uric Acid

6.5.4 Electrocardiogram (ECG)

A standard 12 lead ECG will be performed at Screening/Visit 1 and at the end of study or premature discontinuation visit. Interpretation of the tracing must be made by a qualified physician and documented on the ECG section of the CRF. Each ECG tracing should be labeled with the study and subject number, date, and kept in the source documents at the study site. Clinically significant abnormalities should also be recorded on the Medical History/Adverse event CRF page. Clinically significant findings must be discussed with the Novartis Medical Monitor prior to enrolling the patient in the study.

6.5.5 Pregnancy and assessments of fertility

A urine pregnancy testing will be performed only at screening for the WOCBP.

6.5.6 Appropriateness of safety measurements

The safety assessments selected are standard for this indication/patient population.

6.6 Other assessments

Standard Ophthalmological Examination

In each study visit, a standard ophthalmological examination will be performed to both eyes by using a slit lamp for stereoscopic fundus biomicroscopy and indirect stereo ophthalmoscopy. If needed, the pupil will be dilated by eye drops (ex: tropicamide)

Tonometry

In each study visit, tonometry will be performed to measure the intraocular pressure. IOP will be measured before each injection and 60 minutes (± 10 minutes). In any time during the study, if a significant increase in IOP (≥ 30 mm Hg) is seen in a patient, the patient should be followed closely according to the investigator's decision and additional IOP evaluations should be performed. The patient will leave the study site, after 60 minutes if any safety problems are not seen. If any safety problems or a sudden toxicity occurs, the patient will stay at the study site and will be followed according to the investigator's decision.

6.6.1 Resource utilization

Not applicable for this study.

6.6.2 Health-related Quality of Life

Visual Function Questionnaire – 25 (VFQ – 25), will be completed at the selected sites at visits Baseline/Visit 2, and 12. month. VFQ-25, is a questionnaire consists of 25 questions aiming to evaluate the general visual function of the patients. VFQ-25 will be applied by the

investigator. VFQ-25 scores will be calculated according to the related guidelines. (Mangione et al. 1998, 2001).

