3.1 Study design

This is a randomized controlled, multicenter, 12 month study of Lucentis (ranibizumab) that the consenting patients will participate in a screening period and will be evaluated for their eligibility to enroll the study. After the screening period and the eligibility assessment of the patient, only one eye will be selected / treated as the study eye. After eligibility confirmation at baseline, patients will be randomized into one of the treatment arms as below:

- Arm 1 - Labeled regime arm: Treatment will be given monthly and will be continued until maximum visual acuity is achieved (the patient's visual acuity is stable for three consecutive monthly assessments performed while on ranibizumab treatment). Thereafter patients should be monitored monthly for visual acuity.
- Retreatment criteria:
 - According to this protocol VA stability means BCVA \geq 84 letters (approximate Snellen equivalent of 20/20) or OCT <300 microns in the last 2 consecutive visits or no improvement can be achieved according to the investigators evaluation regarding VA and OCT measures in the last 2 visits . Stable patients do not require reinjection and should be evaluated in the next visit for reinjection.
 - If VA decreases \geq 5 letters compared to previous visit and OCT is >300 microns, patients will be retreated.
 - If VA decreases \geq 5 letters compared to the previous visit or CRT increases >50 microns compared to the previous visit, patients will be retreated.
 - After 3 monthly injections of the investigational drug laser photocoagulation can be administered if VA worsens \geq 10 letters and/or CRT increases >100 microns.
- The interval between two doses should not be shorter than 1 month.
- Arm 2 - Wait and Extend regime arm: Lucentis (ranibizumab) 0.5 mg will be injected subsequently at baseline, month 1 and 2. After the three initial loading doses, patients will be called for the control visits 1 month later. If the visual acuity has reached a stable level and there is no sign of edema on OCT, patients will not receive intravitreal injection and will be called to come back 6 weeks later. The interval is increased by 2 weeks until a maximum of 8 weeks as long as the patient presents as stable regarding visual acuity, central retinal thickness and clinical findings. If there is a negative change, the interval is shortened back to 4 weeks.

Retreatment criteria:

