5.3 Treatment assignment, randomization

At Visit “2” an eligible patient will be given the lowest available randomization number. This number assigns the patient to one of the treatment arms. The investigator will enter the randomization arm on the CRF. Randomization will be performed in 1:1 ratio.

The randomization numbers will be generated using the following procedure to ensure that treatment assignment is unbiased and concealed from patients and investigator staff. A randomization list will be produced by or under the responsibility of the CRO via a special randomization scheme prepared study specific for this study.

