5.4 Treatment blinding

The study is an open label study so there are no blinding procedures applicable.

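### The VFQ-25 is applied by the unmasked investigator on the day of randomisation with no rule that it comes first, and open label is read as ruling out masked reading of BCVA

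*Protocol*

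**What the plan says.** **VFQ-25.** Protocol 6.6.2 says the questionnaire "will be completed at the selected sites at visits Baseline/Visit 2, and 12. month". It adds that "VFQ-25 will be applied by the" investigator (the sentence runs over a page break). The objective it serves, in Section 2.2, is to describe change in function as reported by the patient.

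**Visit 2.** Under Section 5.3, at Visit 2 "an eligible patient will be given the lowest available randomization number", and the investigator enters the arm on the CRF. The schedule in Section 6 also places the first injection at Visit 2. Section 6.2 says that if all other assessments were done at Visit 1, only the VFQ-25 and the injection data remain to be completed at Visit 2.

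**Other statements on timing and sites.** Note i to the schedule says "VFQ-25 will be questioned in either of the first two screening visits" and sets no site limit. SAP 6.14.4 compares scores from the first visit and Month 12.

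**Masking.** Section 5.4 says: "The study is an open label study so there are no blinding procedures applicable". For the primary outcome, Section 6.4 says "VA measurements will be performed in a sitting posture with a scale like ETDRS" and names no masked examiner. For OCT it says "Those evaluations will be performed by the trained staff in each study site". Section 3.1 defines stability partly as a state where "no improvement can be achieved according to the investigators evaluation regarding VA and OCT measures in the last 2 visits". Section 8.5 requires no adjudication committee.

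**The concern.** The VFQ-25 should record the patient's own view. Here it is asked by the person who knows the arm and judges stability, possibly after the patient has learned the arm. A baseline answer given after allocation is not a true baseline, and a Month 12 answer given to the investigator may be softened out of courtesy or expectation.

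The same reasoning applies with more weight to BCVA. A letter score depends on effort and on how far the examiner encourages guesses. BCVA at Month 12 is the primary variable and is compared between arms. Section 5.4 moves from open treatment to no masking of any kind, which does not follow: the regimen can be open while the chart is read by someone not told the arm. A difference in prompting between arms would shift the estimate, and recruiting more patients would not remove the shift.

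**Working it through.** **1. The VFQ-25 passages side by side**

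| Place | Baseline visit | Sites | Who asks |
|---|---|---|---|
| Protocol 6.6.2 | Visit 2 | the selected sites | investigator |
| Protocol Section 6, schedule and note i | Visit 1 or Visit 2 | no limit | not stated |
| Protocol 6.2 | Visit 2, if all else was done at Visit 1 | no limit | not stated |
| SAP 6.14.4 | first visit | no limit | not stated |

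Visit 1 precedes randomisation, so a VFQ-25 taken then cannot be affected by the arm. A VFQ-25 taken at Visit 2 can be, because no passage orders it before assignment. Sections 6.2 and 6.6.2 both point to Visit 2, so this is an expected route and not a rare one. For those patients the first-visit score named in SAP 6.14.4 would also not exist.

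**2. How the VFQ-25 is used.** Section 2.2 sets a descriptive objective and Section 9.5.4 plans descriptive statistics. SAP 6.14.4 applies a Wilcoxon signed rank test separately in each arm. No between-arm test is planned.

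**3. The plan's own sample size (Protocol 9.7, SAP 5.1).** Inputs: margin 5 letters, SD 7, level 0.025, power 90%, and a true difference of zero (not stated, assumed).

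n per arm = 2 × [7 × (1.960 + 1.282) / 5]² = 41.19, so 42 by the normal approximation. With the noncentral t, 42 per arm gives 89.9% and 43 gives 90.6%. The stated 43 per arm (86 in total) is reproduced if 0.025 is one-sided. Read as two-sided, it would need 49 per arm.

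**4. Illustration for BCVA.** The documents give neither size nor direction of bias, so both are assumed. At 43 per arm, SE = 7 × √(2/43) = 1.51 letters. Let b be the assumed assessment bias in letters.

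- Bias toward wait-and-extend, true deficit 5 letters: chance of a false non-inferiority finding = Φ(b/1.51 − 1.96).
- Bias against wait-and-extend, no true difference: power = Φ((5 − b)/1.51 − 1.96).

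| b (letters) | False non-inferiority | Power |
|---|---|---|
| 0 | 2.5% | 91% |
| 0.5 | 5.2% | 85% |
| 1 | 9.7% | 75% |
| 2 | 26% | 51% |

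The rise is not constant per letter: the first letter adds about 7 percentage points and the second about 17.

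These figures assume a margin test at one-sided 0.025, as the sample size section implies. The analysis sections do not contain that test: SAP 6.14.1 names a Mann-Whitney comparison without a margin, and Protocol 9.4.2 says no special hypothesis is intended.

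**The case against.** Several counter-arguments carry weight.

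- **The VFQ-25 cannot distort a planned comparison of arms.** This stands. A reader might infer that a treatment comparison of quality of life is at risk, but the documents plan none. What remains is the quality of each arm's change score and any informal reading of the two arms side by side.
- **The schedule already permits the VFQ-25 at Visit 1.** True, so the gap concerns only patients assessed at Visit 2. Section 6.6.2 names that visit, however, and Section 6.2 steers patients to it.
- **The site limit is not a masking problem.** This also stands. A reader might treat the selected sites as another route for bias, or put a figure on lost precision. The phrase may simply mean the participating centres, and no number of sites is given, so any such figure would rest on an invented share. It is a wording conflict to reconcile.
- **Masking the examiner is only partial.** Patients know their regimen and the visit intervals differ by design, so patient effort stays unmasked and a patient may reveal the arm. Nothing documents staffing at the roughly 12 centres. This limits what can be asked, but does not justify Section 5.4 ruling out the step altogether.
- **Baseline BCVA may need no masking.** Section 6.2 allows assessments completed at Visit 1 not to be repeated, so that BCVA precedes allocation. The schedule shows no OCT at Visit 2, so a rule on BCVA before OCT would not fit there. The useful place is Month 12.

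A reader might also infer from the table that the trial is biased, or biased in favour of wait-and-extend. The documents support only a risk, of unknown size and in either direction.

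**Conclusion.** The point holds in two parts of different weight.

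**VFQ-25.** The plan has an unmasked investigator apply a patient-reported measure, at a visit where the answer can follow disclosure of the arm, and its statements on visit and sites do not agree. This is clear from the text and needs no assumption. The consequence is modest, because the outcome is secondary and tested only within arms. The change is worth making because it costs almost nothing.

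**BCVA.** The plan rules out masked assessment of an effort-dependent primary outcome for a reason that does not require it. The potential consequence is larger: a bias of 1 letter, a fifth of the margin, would take false non-inferiority from 2.5% to about 10%, or power from about 91% to about 75%, depending on direction. That rests on an assumed bias, SD 7, 43 evaluable patients per arm and a margin test that the SAP does not specify. It shows sensitivity and does not estimate what will happen. A masked examiner can be asked for only as far as existing staff allow.

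**What to change.** **Protocol 6.6.2.** State that the patient completes the VFQ-25. If sight prevents this, an existing site member who does not treat the patient reads it out. Whether self-completion fits the scoring guidance cited there cannot be checked from the documents; if that guidance needs an interviewer, the same non-treating member can ask the questions. Timing: at Visit 1, or at Visit 2 before the randomisation number is assigned, and at Month 12 before that day's examination results are discussed. Apply it to all patients, as the schedule shows, and remove the reference to selected sites.

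**Consistency.** Bring Protocol 6.2, note i of the schedule and SAP 6.14.4 into line. SAP 6.14.4 should define baseline as the score taken before randomisation, whichever of the two visits it came from.

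**Protocol 5.4 and 6.4.** Say that treatment is open, but that at Month 12 BCVA is recorded before OCT and before any treatment decision and, where existing staff allow, by a site member who does not make that decision and is not told the arm. Acknowledge that patients know their regimen and that bias from their side remains.

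**Cost.** Protocol and SAP wording, a site instruction, a small change to visit order and possibly a few more questionnaires. Sites without a second person can still keep the order of measurement. No treatment rule changes.

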6.6.3 Pharmacokinetics

Not applicable for this study.

6.6.4 Pharmacogenetics/pharmacogenomics

Not applicable for this study.

6.6.5 Other biomarkers

Not applicable for this study.

7 Safety monitoring

7.1 Adverse events

An adverse event (AE) is any untoward medical occurrence (i.e., any unfavorable and unintended sign [including abnormal laboratory findings], symptom or disease) in a subject or clinical investigation subject *after providing written informed consent* for participation in the study. Therefore, an AE may or may not be temporally or causally associated with the use of a medicinal (investigational) product.

The occurrence of adverse events should be sought by non-directive questioning of the patient at each visit during the study. Adverse events also may be detected when they are volunteered by the patient during or between visits or through physical examination, laboratory test, or other assessments.

Abnormal laboratory values or test results constitute adverse events only if they fulfill at least one of the following criteria:

- they induce clinical signs or symptoms,
- they are considered clinically significant,
- they require therapy.

Clinically significant abnormal laboratory values or test results should be identified through a review of values outside of normal ranges/clinically notable ranges, significant changes from baseline or the previous visit, or values which are considered to be non-typical in patient with underlying disease. Investigators have the responsibility for managing the safety of individual patient and identifying adverse events. Alert ranges for labs and other test abnormalities are included in Appendix 1.

Adverse events should be recorded in the Adverse Events CRF under the signs, symptoms or diagnosis associated with them accompanied by the following information.

- the CTCAE grade

If CTCAE grading does not exist for an adverse event, use 1=mild, 2=moderate, 3=severe, and 4=life-threatening. CTCAE Grade 5 (death) is not used, but is collected in other CRFs (Study Completion, Death/Survival).

- its relationship to the study treatment (no/yes)
- its duration (start and end dates) or if the event is ongoing an outcome of not recovered/not resolved should be reported.
- whether it constitutes a serious adverse event (SAE)
- action taken regarding study treatment
- whether other medication or therapies have been taken (concomitant medication/non-drug therapy)
- its outcome (not recovered/not resolved; recovered/resolved; recovering/resolving, recovered/resolved with sequelae; fatal; or unknown)

An SAE is any adverse event (appearance of (or worsening of any pre-existing) undesirable sign(s), symptom(s) or medical conditions(s) which meets any one of the following criteria

- is fatal or life-threatening
- results in persistent or significant disability/incapacity
- constitutes a congenital anomaly/birth defect
- requires inpatient hospitalization or prolongation of existing hospitalization, unless hospitalization is for:
 - routine treatment or monitoring of the studied indication, not associated with any deterioration in condition
 - elective or pre-planned treatment for a pre-existing condition that is unrelated to the indication under study and has not worsened since signing the informed consent
 - treatment on an emergency outpatient basis for an event not fulfilling any of the definitions of a SAE given above and not resulting in hospital admission
 - social reasons and respite care in the absence of any deterioration in the patient's general condition
- is medically significant, i.e. defined as an event that jeopardizes the patient or may require medical or surgical intervention to prevent one of the outcomes listed above.

All malignant neoplasms will be assessed as serious under "medically significant" if other seriousness criteria are not met.

Unlike routine safety assessments, SAEs are monitored continuously and have special reporting requirements; see Section 7.2.

All adverse events should be treated appropriately. Treatment may include one or more of the following: no action taken (i.e. further observation only); study treatment dosage adjusted/temporarily interrupted; study drug(s) permanently discontinued; concomitant medication given; non-drug therapy given. The action taken to treat the adverse event should be recorded on the Adverse Event CRF.

Once an adverse event is detected, it should be followed until its resolution or until it is judged to be permanent, and assessment should be made at each visit (or more frequently, if necessary) of any changes in severity, the suspected relationship to the study treatment, the interventions required to treat it, and the outcome.

Information about common side effects already known about the investigational drug can be found in the Investigator Brochure (IB) or will be communicated between IB updates in the form of Investigator Notifications. This information will be included in the patient informed consent and should be discussed with the patient during the study as needed.

The investigator should also instruct each patient to report any new adverse event (beyond the protocol observation period) that the patient, or the patient's personal physician, believes might reasonably be related to study treatment. This information should be recorded in the investigator's source documents; however, if the AE meets the criteria of an SAE, it must be reported to Novartis.

